| Table 2.2 | Staggered Enrolment and Dose Escalation for Groups 2 to 4 (Dose 1) with Minimum Time Intervals* | 16 |
| Table 8.1 | Protocol CV-7202-104 Dose regimen | 37 |
| Table 9.1 | Intensity Grading for Solicited Local AEs (Days 1 to 8) | 39 |
| Table 9.2 | Intensity Grading* for Solicited Systemic AEs (Days 1 to 8) | 40 |
| Table 9.3 | Timing and Maximum Volumes of Blood Draws | 54 |
| Table 12.1 | Protocol-Required Safety Laboratory Assessments | 73 |
| Table 12.2 | List of Names and Addresses | 74 |

List of Figures

| | | |
|------------|--------------------------------|----|
| Figure 5.1 | CV-7202-104 Trial Design | 23 |
|------------|--------------------------------|----|

1 Synopsis

| | |
|---|--|
| Protocol Title: | A non-randomized, open label, controlled, dose-escalation, phase I clinical trial to evaluate the safety, reactogenicity and immunogenicity of one or two administrations of candidate rabies mRNA vaccine CV7202 in healthy adult subjects |
| Short Title: | Safety, reactogenicity and immunogenicity of CV7202 in healthy adult subjects |
| Rationale: | The objectives of this phase I trial are to assess the safety and reactogenicity of CV7202 in the context of immune responses to rabies virus glycoprotein (RABV-G) in order to select the optimal dose and number of doses. The dose range selected is intended to provide data for defining the optimal dosage of CV7202 to be tested in subsequent clinical trials. |
| Sponsor: | CureVac AG [name] [name] Germany |
| Coordinating/Principal Investigator: | |

Trial Objectives and Endpoints:

| Objectives | Endpoints |
|--|--|
| Primary | |
| 
To assess the safety and reactogenicity profile of CV7202 administered intramuscularly (i.m.) to healthy adults (18–40 years old), as a range of doses (1, 2 and 5 µg) in one- or two-dose regimens. | 
The percentages of subjects with, and the frequencies and intensities of solicited local adverse events (AEs) reported on the day of vaccination and the 7 subsequent days (Days 1–8). |
| | 
The percentages of subjects with, and the frequencies, intensities and relationship to vaccination, of solicited systemic AEs reported on the day of vaccination and the 7 subsequent days (Days 1–8). |
| | 
The duration (in days) of solicited local AEs, of solicited systemic AEs and of the individual solicited AEs. |

| | |
|--|---|
| | 
 The percentages of subjects with and frequencies and intensities of any unsolicited and related unsolicited AEs reported on the day of vaccination and the 28 subsequent days (Days 1-29). |
| | 
 The percentages of subjects with and frequencies and relationship to vaccination of any serious adverse events (SAEs) and any medically-attended AEs (MAAEs) up to 12 months post last dose. |
| | 
 The percentages of subjects with and frequencies and relationship to vaccination of any adverse events of special interest (AESIs) up to 12 months post vaccination. |
| Secondary | |
| For safety: | |
| 
 To assess the safety profile of CV7202 administered i.m. to healthy adults (18-40 years old), as a range of doses (1, 2 and 5 µg) in one- or two-dose regimens in the period from 12 to 24 months post last dose. | 
 The percentages of subjects with and frequencies of SAEs and MAAEs related to study vaccination from 12 months post last dose up to 24 months post last dose (trial end). |
| | 
 The percentages of subjects with and frequencies and relationship to vaccination of any AESIs from 12 months post last dose up to 24 months post last dose (trial end). |
| For the characterization of the humoral immune response: | |
| 
 To evaluate the potential protective immune responses to CV7202 and Rabipur® in healthy adults (18-40 years old), by assessing the percentages of subjects with rabies-specific serum virus-neutralizing antibody titers (VNTs) ≥ 0.5 IU/ml. | 
 Percentages of subjects with rabies-specific serum VNTs ≥ 0.5 IU/ml by trial group on Days 1 (pre-vaccination), 15, 43, and 12, 18* and 24* months post last dose. 
* Will be performed only in subjects with detectable RABV-G-specific IgG at 6 months after the last vaccination or Day 91 if the Month 6 blood sample is not available.
 |

| | |
|---|--|
| 
 To evaluate the immunogenicity (VNTs) of CV7202 administered to healthy adults (18–40 years old), as a range of doses (1, 2 and 5 µg) in one- or two-dose regimens and the immunogenicity of Rabipur® administered in a 3-dose regimen. | 
 Serum geometric mean titers (GMTs) of virus-neutralizing antibodies by trial group on Days 1, 8, 15, 29, 36, 43, 57, 91, and 6, 12, 18* and 24* months post-last dose. 
* Will be performed only in subjects with detectable RABV-G-specific IgG at 6 months after the last vaccination or Day 91 if the Month 6 blood sample is not available.
 |
| Exploratory | |
| For the evaluation of the innate immune response: | |
| 
 To evaluate the innate immune response to one or two doses of CV7202 compared with baseline. | 
 Serum cytokine concentrations*, including but not limited to CXCL10, CCL3, IL-6, TNF-α and IFN-γ, at pre-vaccination and 4 hours post-vaccination on Day 1, and Days 2 or 3** and 8 after each vaccination. |
| | 
 Transcriptome profiling* on the day of vaccination at pre-vaccination, and Days 2 or 3** and 8 after each vaccination. 
* Will be performed in the first 5 subjects in Group 2 (** on Day 3) and all subjects in Groups 3 and 4 (** on Day 2). Note that Day 3 was planned in the original protocol and only applies to subjects in Group 2 who were already enrolled and vaccinated before this protocol amendment was issued. Day 2 applies to all other subjects.
 |
| For the evaluation of antigen specific T-cell response: | |
| 
 To evaluate the frequencies and functionalities of RABV-G-specific T cells after one or two doses of CV7202 compared with baseline. | 
 The frequencies and functionalities of RABV-G-specific T cells in peripheral blood from the first 5 subjects in Group 2 and all subjects in Groups 3 and 4 on Days 1, 8, 36, 91*, and 6* and 12* months post-last dose. 
* For groups that have shown a significant T-cell response at Day 8 or 36 compared to baseline.
 |
| For the evaluation and characterization of the B-cell response: | |
| 
 To evaluate the frequencies of RABV-G-specific B cells after one or two doses of CV7202 compared with baseline. | 
 The frequencies of RABV-G-specific B cells in peripheral blood from the first 5 subjects in Group 2 and all subjects in Groups 3 and 4 on Days 1, 8, 36, 91*, and 6* and 12* months post-last dose. |

| | |
|---|--|
| 
 To evaluate the effect of vaccination on B-cell phenotype and activation after one or two doses of CV7202 compared with baseline. | 
 The frequencies and activation status of phenotypically distinct subsets of B cell populations, including but not limited to naïve and memory B cells, plasmablasts and plasma cells for the first 5 subjects in Group 2 and all subjects in Groups 3 and 4 on Days 1, 8, 36, 91*, and 6* and 12* months post-last dose. |
| 
 To evaluate the effect of vaccination on B-cell clonality after one or two doses of CV7202 compared with baseline. | 
 Sequencing of B-cell receptors (BCR) of circulating B cells on Days 1, 8, 29, 36, 57, 91*, and 6* and 12* months post-last dose. 
* For groups that have shown a significant B-cell response at Day 8 or 36 compared to baseline.
 |

For the characterization of the humoral immune response:

| | |
|--|---|
| 
 To evaluate RABV-G-specific antibody responses throughout the trial including the follow-up period by assessing IgM, IgG and IgA levels. | 
 RABV-G-specific IgM, IgG and IgA levels measured by ELISA on Days 1, 8, 15, 29, 36, 43, 57, 91, and 6 and 12 months post-last dose. RABV-G-specific IgG levels measured by ELISA 18* and 24* months post-last dose. 
* Will be performed only in subjects with detectable RABV-G-specific IgG at 6 months after the last vaccination or Day 91 if the Month 6 blood sample is not available.
 |
| 
 To characterize the nature and quality of the RABV-G-specific antibody response, by measuring the serum affinity and avidity after one or two doses of CV7202 and the breadth of neutralization against heterologous lyssaviruses with variant epitopes. | 
 Identification of epitopes recognized by vaccine-induced antibodies on Days 1, 15, 43, and 12 months post last dose*. Measurement of RABV-G-specific antibody avidity and affinity on Days 1, 15, 43, and 12 months post last dose*. Measurement of VNTs against additional heterologous lyssaviruses on Days 1, 15, 43, and 12 months post last dose*. 
* Will be performed only on selected samples with VNT >0.5 IU/ml.
 |

Overall Design:

This is a non-randomized, open label, controlled, dose-escalation, phase I clinical trial to evaluate the safety, reactogenicity and immunogenicity of one or two i.m. administrations of candidate rabies mRNA vaccine CV7202 in healthy adult subjects. The subjects will be enrolled sequentially in up to 4 trial groups to receive either a dose of CV7202 containing different mRNA content or Rabipur®. In a first CV7202 group, 10 subjects have received a dose containing 5 µg mRNA. A dose of 1 or 2 µg mRNA will be administered to 2 additional

| | 
groups of 16 subjects each, of whom 8 in each group will be administered a second dose 28 days later.
 
A control group of 10 subjects will receive 3 doses of the licensed vaccine Rabipur® according to the manufacturer's recommendations. Safety and immunogenicity assessments will be made up to 2 years following the last dose administration. Specified safety data will be reviewed by an internal safety review committee (iSRC) and a data safety monitoring board (DSMB) on a pre-defined schedule.
 | | | | | |
|--|--|----------------------|--------------------|---------------|--------------|---------------|
| Trial Population Key Inclusion Criteria: | 
 1. Healthy male and female subjects aged 18 to 40 years inclusive. 2. Expected to be compliant with protocol procedures and available for clinical follow-up through the last planned visit. 3. Physical examination and laboratory results without clinically significant findings. 
The full list of inclusion criteria is provided in the protocol.
 | | | | | |
| Trial Population Key Exclusion Criteria: | 
 1. Receipt of licensed or investigational rabies vaccine prior to the administration of the trial vaccine. 2. History of potential immune mediated disease. 3. Known allergy to any component of CV7202 or Rabipur®. 
The full list of exclusion criteria is provided in the protocol.
 | | | | | |
| Number of Subjects: | 
Approximately 52 subjects will be enrolled.
 | | | | | |
| Vaccination Groups and Duration: | | Trial Product | Composition | Dosing | | |
| | | | | Day 1 | Day 8 | Day 29 |
| | | | | N | N | N |
| Group 1 | Rabipur® | N/A | | 10 | 10 | 10 |
| Group 2* | | 5 µg mRNA | 10 | | | N/A |
| Group 3 | | 1 µg mRNA | 16 | | | 8 |
| • Group 3a** | | | | | | |
| Group 4 | | 2 µg mRNA | 16 | | | 8 |
| • Group 4a** | | | | | | |
| Total CV7202 | | | | 42 | | 16 |
| 
* Note that enrolment in Group 2 was already completed at the time this protocol amendment was issued.
 
** 'a' groups are a subset consisting of 8 subjects of Groups 3 and 4 scheduled to receive a first dose on Day 1 and a second dose on Day 29.
 | | | | | | |
| Measurements and Assessments: | 
Due to the exploratory nature of this trial only descriptive statistics will be used, no confirmatory statistical inference will be performed.
 
Safety set: This is the subset of subjects, who have received at least one dose of the candidate rabies mRNA vaccine CV7202 or the active control Rabipur® and for whom any post-Day 1 safety data are available. The analysis of safety will be performed on this population.
 
Full-analysis (FA) set: This is the subset of the Safety Set with subjects who have the baseline sample and at least one additional blood sample available for VNT analysis. This analysis set is the primary analysis set for all immunogenicity objectives.
 | | | | | |

| | |
|--|--|
| | 
Primary and secondary safety and reactogenicity will be assessed as follows:
 
1. AEs (type, intensity, frequency and relationship to vaccination), i.e. incidence and severity of AEs for both solicited local and systemic events (reported on the day of vaccination and the 7 subsequent days [Days 1-8]) and unsolicited events (reported on the day of vaccination and the 28 subsequent days [Days 1-29]).2. SAEs, MAAEs and AEs leading to trial or vaccine withdrawal up to 12 months post last dose. After Visit 15 (Month 12), only SAEs and MAAEs that according to the investigator are considered to be related to study vaccination will be collected.3. Intercurrent medical conditions and AESIs throughout the trial.4. Local reactogenicity assessment of injection site in all subjects. 
Further safety assessments will be conducted based on vital signs and laboratory assessments. Results will be summarized in tables and supported by subject level listings.
 
Secondary immunogenicity endpoints:
 
1. Number and percentage of subjects having VNTs ≥ 0.5 IU/ml on Days 1, 15, 43, and 12, 18 and 24 months post last dose.2. Individual functional antibody titers, GMTs and range of titers in sera collected on Days 1, 8, 15, 29, 36, 43, 57, and 12, 18 and 24 months post last dose. 
Further immunogenicity assessments will be based on VNTs, RABV-G-specific immunoglobulins (Ig) IgG, IgM and IgA serum antibodies and other immunogenicity-related parameters throughout the duration of the trial. Results will be summarized in tables, figures and supported by subject level listings.
 
No statistically-based sample size estimation was performed.
 |
|--|--|

2 Schedule of Activities

Table 2.1 Schedule of Activities

| Visit Type | Procedure | References | Pre-screening | Screening | Clinic visit | | Phone call | Clinic visit | | | | Phone call | Clinic visit | | | | Clinic visit*** | | | | | | | | |
|--|--|------------|---------------|------------|--------------|---------|------------|--------------|-------|-------|-------|------------|--------------|-------|-------|-------|-----------------|--------|---------|--------|---------|--------|---------|--------|----------|
| | | | -90 to -1* | -30 to -1* | 1 | 2† | 3 | 8 | 10 | 15 | 29 | 30#† | 31 | 36 | 43 | 57 | 91 | M6 | | M12 | | M18 | | M24 | |
| | | | N/A | N/A | N/A | +/- 2** | - | +1 | -1/+2 | -1/+2 | +/- 2 | +/- 2** | - | -1/+2 | +/- 2 | +/- 2 | +/- 7 | +/- 14 | + 15-90 | +/- 30 | + 31-90 | +/- 30 | + 31-90 | +/- 30 | + 31-180 |
| Visit Number | Visit Window (days) | Visit Type | 1 | 2 | 3 | 4 | - | 5 | 6 | 7 | 8 | 9 | - | 10 | 11 | 12 | 13 | 14 | 14A | 15 | 15A | 16 | 16A | 17 | 17A |
| Signed Informed Consent ^a | 9.4.1 | | | | | | | | | | | | | | | | | | | | | | | | |
| Medical History | 9.4.1 | | | | | | | | | | | | | | | | | | | | | | | | |
| Inclusion/Exclusion criteria | 6.1, 6.2, 9.4.1, 9.4.2, 9.4.3 | | | | | | | | | | | | | | | | | | | | | | | | |
| Vaccine delay recommendations | 6.3, 9.4.3, 9.4.6, 9.4.9 | | | | | | | | | | | | | | | | | | | | | | | | |
| Demographics | 9.4.1 | | | | | | | | | | | | | | | | | | | | | | | | |
| Pregnancy Test | 9.4.2, 9.4.3, 9.4.6, 9.4.9 | | | | | | | | | | | | | | | | | | | | | | | | |
| Vaccination | | | | | | | | | | | | | | | | | | | | | | | | | |
| CV7202 | 9.4.3, 9.4.9 | | | | | | | | | | | | | | | | | | | | | | | | |
| Rabipur® | 9.4.3, 9.4.6, 9.4.9 | | | | | | | | | | | | | | | | | | | | | | | | |
| Safety monitoring | | | | | | | | | | | | | | | | | | | | | | | | | |
| Physical Examination ^e | 9.4.2-9.4.11, 9.4.14, 9.4.15, 9.4.17, 0 | | | | | | | | | | | | | | | | | | | | | | | | |
| 12-lead Electrocardiogram | 9.4.2 | | | | | | | | | | | | | | | | | | | | | | | | |
| Vital signs ^f | 9.4.1, 9.4.3-9.4.11, 9.4.17, 0 | | | | | | | | | | | | | | | | | | | | | | | | |
| Post-injection vaccination site reactogenicity assessment ^g | 9.4.3-9.4.7, 9.4.9-9.4.10 | | | | | | | | | | | | | | | | | | | | | | | | |
| Diary dispensed/training ^h | 9.4.3, 9.4.5, 9.4.9 | | | | | | | | | | | | | | | | | | | | | | | | |
| Diary review/reminder ^h | 9.4.4-9.4.14 | | | | | | | | | | | | | | | | | | | | | | | | |
| Diary collection ^h | 9.4.5, 9.4.9, 9.4.14 | | | | | | | | | | | | | | | | | | | | | | | | |
| Assess all post-dose solicited AEs | 9.4.3-9.4.12 | | | | | | | | | | | | | | | | | | | | | | | | |
| Assess all post-dose unsolicited AEs | 9.4.3-9.4.14 | | | | | | | | | | | | | | | | | | | | | | | | |
| Assess all SAEs | 9.4.3-9.4.17 | | | | | | | | | | | | | | | | | | | | | | | | |
| Assess all MAAEs | 9.4.3-9.4.17 | | | | | | | | | | | | | | | | | | | | | | | | |
| Assess AEs leading to premature withdrawal | 9.4.3-9.4.17 | | | | | | | | | | | | | | | | | | | | | | | | |
| Assess intercurrent medical conditions | 9.4.3-0 | | | | | | | | | | | | | | | | | | | | | | | | |
| Assess Concomitant Medications/Vaccinations | 9.4.2-0 | | | | | | | | | | | | | | | | | | | | | | | | |
| Assess AESIs | 9.4.3-0 | | | | | | | | | | | | | | | | | | | | | | | | |
| Assess SAEs related to study vaccination ^m | 9.4.3-0 | | | | | | | | | | | | | | | | | | | | | | | | |
| Assess MAAEs related to study vaccination ^m | 9.4.3-0 | | | | | | | | | | | | | | | | | | | | | | | | |
| Safety Lab ⁱ (~9 ml) | 9.4.2-9.4.5, 9.4.8-9.4.11, 9.4.14-9.4.17 | | | | | | | | | | | | | | | | | | | | | | | | |
| TSH, Thyroid antibodies, ANA (~3 ml) [§] | 9.5.2 | | | | | | | | | | | | | | | | | | | | | | | | |
| Immunogenicity | | | | | | | | | | | | | | | | | | | | | | | | | |
| VNTs (serum) ^l (~18ml) | 9.4.3, 9.4.5, 9.4.8, 9.4.9, 9.4.11-0 | | | | | | | | | | | | | | | | | | | | | | | | |
| IgM/ IgG/ IgA ELISA (serum) ^l (~6 ml) | 9.4.3, 9.4.5, 9.4.8, 9.4.9, 9.4.11-0 | | | | | | | | | | | | | | | | | | | | | | | | |
| Cellular immune response and leukocyte phenotyping (PBMCs) ^{i, l} (~40-60 ml) | 9.4.3, 9.4.5, 9.4.11, 9.4.15-9.4.17 | | | | | | | | | | | | | | | | | | | | | | | | |
| Cytokine assessment (serum) ^{i, l} (~6 ml) | 9.4.3-9.4.5, 9.4.9-9.4.11 | | | | | | | | | | | | | | | | | | | | | | | | |
| Transcriptome profiling (PBMCs) ^{i, l} (~10ml) | 9.4.3, 9.4.4, 9.4.9, 9.4.10 | | | | | | | | | | | | | | | | | | | | | | | | |
| Immune receptor sequencing (PAXgene DNA) ⁱ (~5ml) | 9.4.3, 9.4.5, 9.4.9, 9.4.11, 9.4.14-9.4.17 | | | | | | | | | | | | | | | | | | | | | | | | |
| Maximum total blood volume (ml) | Table 9.3 | 3 | 11 | 120 | 25 | 0 | 94 | 0 | 33 | 60 | 25 | 0 | 94 | 24 | 38 | 78 | 78 | 78 | 78 | 24 | 24 | 24 | 24 | | |
| Trial end | | | | | | | | | | | | | | | | | | | | | | | | | |

Notes:

M6 corresponds to Day 181 (1-dose groups) and Day 209 [2-dose groups and Group 1 (Rabipur®)].

M12 corresponds to Day 365 (1-dose groups) and Day 393 [2-dose groups and Group 1 (Rabipur®)].

M18 corresponds to Day 547 (all groups).

M24 corresponds to Day 729 (all groups).

Vaccinations planned at Visit 3 (Dose 1 for Groups 1 to 4), Visit 5 (Dose 2 Rabipur® for Group 1), Visit 8 (Dose 2 for Groups 3a and 4a, Dose 3 Rabipur® for Group 1).

* The pre-screening and screening visits can be performed on the same day.

** The Day 2 and Day 30 visits should be performed at around 24 +/- 2 hours after the vaccination.

† Note that for subjects in Groups 1 and 2, who were already enrolled and vaccinated before Protocol Amendment 1 was issued, Visit 4 occurred on Day 3 and Visit 9 occurred on Day 31 as planned in the original protocol.

§ Blood drawn at the pre-screening visit will be kept for retrospective measurement of TSH, thyroid antibodies and ANA following the occurrence of clinical autoimmune events (

clinical autoimmune event).

=Only for subjects receiving vaccination (Dose 2 for Groups 3a and 4a, Dose 3 Rabipur® for Group 1)

‡ Two blood samples for cytokine assessment will be drawn on the days of vaccination, including one pre-vaccination sample and one sample at 4 hours post-vaccination (Only for CV7202 groups).

*** The optional Visits 14A, 15A, 16A and 17A should only take place in case the respective visit could not be conducted as described in the protocol. In case Visit 14, 15, 16 or 17 cannot take place on site due to the public health emergency related to COVID-19, safety information should be collected via a phone call within the protocol-allowed time interval for the respective visit. However, if the investigator judges that the benefits of a site visit outweigh the risks based on clinical symptoms, the visit should take place on site. In this case, all procedures as indicated in this table for the respective time point should be performed, if possible. If the information was collected via a phone call, the respective Visit A should be scheduled on site within the protocol-allowed time interval and all indicated procedures, including blood sampling, should be performed. Also, in case the visit was conducted on site but not all procedures could be performed, the respective Visit A should be scheduled on site within the protocol-allowed time interval.

Abbreviations: AE=Adverse event; AESI = Adverse event of special interest; ANA = Antinuclear antibody; ELISA = Enzyme-linked immunosorbent assay; Ig = Immunoglobulin; MAAE = Medically-attended adverse event;

PBMC = Peripheral blood mononuclear cell; SAE = Serious adverse event; TSH = Thyroid-stimulating hormone; VNT = Virus-neutralizing antibody titers;

^a Informed consent form(s) signed prior to any procedures.

^b In women of childbearing potential, serum pregnancy test. A 3 ml blood sample will be taken.

^c In women of childbearing potential, urine pregnancy tests will be performed before each vaccination, unless the serum pregnancy test was performed less than 3 days before.

^d Second vaccination of CV7202 will be given only to 8 subjects in Groups 3 and 4 (i.e. Groups 3a and 4a).

^e Physical examination and vital signs must be performed/analyzed by a qualified healthcare professional.

^f Vital signs to be checked: body temperature, pulse, blood pressure. Vital signs will be measured pre- and post-vaccination prior to discharge. Subjects will be observed for 4 hours following each vaccination; vital signs must be within normal or clinically non-relevant abnormal ranges or have returned to pre-vaccination values for the subject to be discharged from the phase I Unit.

^g All vaccinated subjects will undergo vaccination site reactogenicity assessment at 1 hour post-vaccination on the day of vaccination (Day 1, Day 8 and Day 29) and 1 or 2 days after each vaccination (Day 2 or 3, Day 10 and Day 30 or 31). Note that Days 3 and 31 were planned in the original protocol and only apply to subjects in Groups 1 and 2 who were already enrolled and vaccinated before this protocol amendment was issued. Local reactions (injection site pain, redness, swelling and itching) will be assessed on an intensity scale of absent, mild, moderate and severe.

^h Solicited and unsolicited AE diaries. Solicited AEs occurring on the day of vaccination (Day 1, Day 8 and Day 29) and for the following 7 days will be recorded by the subject on the diary card. The diary card will be reviewed on Day 2 or 3, 8, 10, 15, 29, 30 or 31, 36, 43 and 57. Unsolicited AEs occurring on the day of vaccination (Day 1, Day 8 and Day 29) and for the following 28 days will be recorded by the subject on the diary card.

ⁱ The VNT serum sample is intended as the baseline value and must be taken before vaccination on Day 1 and Day 29.

^j Hematology (complete blood count, including differential and platelets), biochemistry.

^k Coagulation (activated partial thromboplastin time [aPTT]) and prothrombin time/international normalized ratio (INR) will be performed at the following time points: Screening, Day 1, Day 2 or 3 and Day 30 or 31.

^l In the first 5 subjects in Group 2 and all subjects in Groups 3 and 4. 60 ml for the baseline (Day 1) time point, 40 ml for subsequent blood draws.

^m At each study visit/contact preceding Month 18, SAE and MAAEs considered as related to study vaccination were collected as part of all SAEs and MAAEs.

ⁿ At Month 18 and Month 24, VNTs and IgG assessments will be performed only in subjects with detectable RABV-G-specific IgG at 6 months after the last vaccination or Day 91 if the Month 6 blood sample is not available.

^o If no blood sampling could be performed at Visit 15 and the optional Visit 15A, the end-of-trial blood sample for safety assessment may be performed at Visit 17 (Month 24).

Table 2.2 Staggered Enrolment and Dose Escalation for Groups 2 to 4 (Dose 1) with Minimum Time Intervals*

| Week#* | Group #2 | | Groups #3 - #4 | |
|---------|---------------------------------|--------|---------------------------------|--------|
| | Dose 1 (Day 1) | Review | Dose 1 (Day 1) | Review |
| 1 | #1 (enrol) Day 1 | | | |
| | #2 - #3 Day 3 | | | |
| 2 | #4 - #5 Day 1 | iSRC** | | |
| 3 | #6 - #10 (enrol) | | | |
| 7 | DSMB GO/NO GO (next dose level) | | | |
| 8 | | | #1 (enrol) Day 1 | |
| | | | #2 Day 3 | |
| 9 | | | #3 - #4 Day 1 | iSRC** |
| 10 -11 | | | #5 - #16 (enrol) [§] | |
| 12 | | | DSMB GO/NO GO (next dose level) | |
| 13 - 42 | | | Enrolment cycle for Group 4† | |

DSMB (Data safety monitoring board) provides recommendation to proceed or not with dose-escalation; iSRC = Internal safety review committee; Day 1 corresponds to Monday, Day 3 corresponds to Wednesday.
* These intervals may be prolonged at the discretion of the investigator or upon request of the sponsor or DSMB for safety or operational reasons;
** The iSRC will take place only once the last subject in the sentinel group (first 5 subjects of Group 2, first 4 subjects in Groups 3 and 4 and subsequent 6 subjects in Groups 3 and 4) has been vaccinated and followed up for at least 2 working days.
§ The staggered enrolment for the initial 4 subjects may be extended to the subsequent subjects in Groups 3 or 4. The number of subjects in this extended staggered enrolment may be further established by the investigator, sponsor or DSMB based on the data obtained in earlier enrolled subjects in these groups.
† Enrolment in Group 4 can proceed as for Group 3 with a duration of a minimum of 7 weeks. A slower enrolment schedule can be followed in agreement with the investigator and sponsor, if needed with input from the iSRC or DSMB.

3 Introduction

Rabies is a viral zoonosis which causes acute encephalitis in mammals including humans. The disease is virtually always fatal once clinical symptoms develop. There are an estimated 59 000 rabies-related deaths each year [2]. The virus is endemic worldwide, but human mortality due to rabies differs markedly from continent to continent [3]. Recognizing that rabies remains a neglected disease in Asia and Africa despite the existence of safe and effective vaccines, the World Health Organization (WHO) Strategic Advisory Group of Experts on Immunization (SAGE), established a working group on rabies vaccines and immunoglobulins (Igs) in 2016 to review scientific evidence, programmatic considerations and vaccine regimens of existing therapies, and also to evaluate the potential impact of new biologicals [4].

Existing rabies vaccines can be used for both pre-exposure and post-exposure prophylaxis. Although pre-exposure prophylaxis is primarily used by animal handlers, laboratory personnel, veterinarians and forestry workers in Europe and North America, rabies prophylaxis is also appropriate for travelers to high-risk regions [5].

The US Centers for Disease Control and Prevention (CDC) reported a range of approximately 16–200 possible exposures per 100 000 travelers [6], while a 2008 study from Thailand assessed the risk of rabies exposure among 870 backpackers and found that 3.6% of them had been licked and 0.7% had been bitten by an animal [7]. Despite the demonstrated risk of rabies exposure to travelers in high-risk regions, compliance with the three injection primary vaccination series is suboptimal. Gautret and Parola reported that 76% of travelers for whom vaccination was recommended by the travel clinic physician either declined vaccination or did not have time to complete the primary three-dose vaccination series [8]. Similarly, in canine rabies infected areas, such as countries of Southeast Asia, pre-exposure prophylaxis of children has been proposed but not implemented. Children under the age of 15 are the most frequently exposed, representing 40% of human exposures [9], and would benefit from pre-exposure prophylaxis. A study assessing pre-exposure prophylaxis against rabies among school-aged children in Bangalore, India, suggests that this approach may be a useful tool for protecting children in highly endemic regions [10].

Although safe and effective, existing vaccines have limitations: they require refrigeration, a three-injection primary series for pre-exposure prophylaxis and virus inactivation steps during manufacturing which may lead to lot failure. In recognizing the ongoing need for an effective and convenient rabies vaccine, CureVac proposes to apply its proprietary messenger ribonucleic acid (mRNA) platform to develop a shelf-stable, polyethylene-free, safe and effective vaccine which can be used for both pre-exposure and post-exposure prophylaxis in humans.

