In Groups 3 and 4, the first 4 subjects will also be enrolled using a staggered approach. The first 4 subjects will sequentially receive the first dose with a 2 working-day interval between subject #1 (e.g. Week 1 – Day 1 – Monday) and subject #2 (e.g. Week 1- Day 3 – Wednesday) and will be observed for 2 days. A phone call will be performed after 2 days to collect safety information. Subjects #3 and #4 will receive their first dose at the earliest one week after subject #1 (e.g. Week 2 – Day 1 – Monday). All data obtained from these sentinel subjects (at least until 2 days after the vaccinations) must be entered continuously into the eCRF, at the latest within 24 hours, to allow a timely safety assessment. Once the fourth subject in the group has been vaccinated and followed up for at least 2 working days, safety data recorded in the eCRF for the first 4 subjects will be reviewed by the iSRC. Following iSRC approval, the remaining 12 subjects in the group will be enrolled and receive the first dose. In addition, the staggered enrolment may be extended to the subsequent subjects to be enrolled in Groups 3 and 4. The number of subjects in this extended staggered enrolment may be further established by the investigator, sponsor or DSMB based on the data obtained in earlier enrolled subjects in these groups. The DSMB will review safety data for an observation period of 28 days following administration of the first dose for all subjects in each dose group prior to enrolment into the next dose group (i.e. from the 1 µg dose level Group 3 to the 2 µg dose level Group 4). Before administration of the second dose of CV7202, the iSRC will review all available accumulated safety data from all subjects having already received a second dose.

Enrolment in each dose group can proceed as follows for a duration of a minimum of 7 weeks per group. A slower enrolment schedule can be followed in agreement with the investigator and sponsor, if needed with input from the iSRC or DSMB:

- **Week 1:** Start enrolment in Group 3 (up to 2 subjects). Subject #1 on Day 1, subject #2 on Day 3.
- **Week 2:** Enrol subjects #3 and 4 on Day 1 and prepare iSRC review of AEs and available safety data following 2 days' observation.
- **From Week 3:** Enrol the remainder of the subjects (i.e. 12 subjects for Groups 3 and 4). Extended staggered enrolment (e.g. for subjects #5 to 10 or beyond) can be implemented as needed.

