- **From Week 7:** Collect solicited AEs, unsolicited AEs, SAEs and safety laboratory data, and prepare DSMB review.
- Favorable DSMB decision: Start the enrolment cycle for the next dose level group.

The staggered approach to dose administration does not apply to Dose 2.

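### Table 2.2 schedules the Group 3 DSMB decision for Week 12, when at most 2 of 16 subjects can have the 28 days of follow-up that section 5.1.1 requires for all of them

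*Protocol*

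**What the plan says.** **Section 5.1.1 (Dose-finding Schedule, Enrolment Plan).** Before a further dose level opens, what the DSMB looks at must cover "an observation period of 28 days following administration of the first dose for all subjects in each dose group prior to enrolment", meaning enrolment of the following dose level. The section names the step from Group 3 (1 µg) to Group 4 (2 µg) as the case in point. It adds: "Enrolment in each dose group can proceed as follows for a duration of a minimum of 7 weeks per group". From Week 7 of the group's cycle the task is: "Collect solicited AEs, unsolicited AEs, SAEs and safety laboratory data, and prepare DSMB review". The next group then depends on the outcome: "Favorable DSMB decision: Start the enrolment cycle for the next dose level group".

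**Table 2.2.** The title says that the intervals are minimums, and the key sets Day 1 as Monday and Day 3 as Wednesday. For Group 3:

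- Week 8: #1 on Monday, #2 on Wednesday
- Week 9: #3 and #4 on Monday
- Weeks 10 to 11: the remaining twelve, "10 -11 | | | #5 - #16 (enrol"
- Week 12: "12 | | | DSMB GO/NO GO (next dose level"
- Weeks 13 to 42: the Group 4 cycle

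The asterisk footnote says: "These intervals may be prolonged at the discretion of the investigator or upon request of the sponsor or DSMB for safety or operational reasons". The dagger footnote says: "Enrolment in Group 4 can proceed as for Group 3 with a duration of a minimum of 7 weeks".

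**The concern.** The Week 12 row follows directly after a two-week block in which 12 of the 16 Group 3 subjects receive their first dose. Those subjects cannot have four weeks of observation one or two weeks later, yet section 5.1.1 makes four weeks in every subject the condition for opening the next dose level.

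Section 5.1.1 itself points to Table 2.2 as the staggering plan that protects subjects, so the table is meant to be followed. A DSMB meeting held at the tabulated minimum would decide on escalation from 1 to 2 µg without the full 28-day unsolicited-AE window for at least 14 of 16 subjects (16 − 2 = 14).

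**Working it through.** **Inputs.** Dosing weeks, weekday key and DSMB weeks come from Table 2.2. The 28-day rule, the 7-week minimum and the Week 7 preparation step come from section 5.1.1.

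**Calendar.** Let Monday of Week w be day 7(w − 1). A subject qualifies when the review day minus the dosing day is at least 28. This matches the unsolicited-AE window, which is the vaccination day plus the 28 days after it.

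**Check on Group 2, same table.** Last enrolment is in Week 3 and the DSMB in Week 7: (7 − 3) × 7 = 28 days on the same weekday. The Group 2 rows satisfy the rule.

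**Group 3.**

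| Subjects | Dose 1 | Day | Day + 28 | Falls on |
|---|---|---|---|---|
| #1 | Week 8 Monday | 49 | 77 | Week 12 Monday |
| #2 | Week 8 Wednesday | 51 | 79 | Week 12 Wednesday |
| #3, #4 | Week 9 Monday | 56 | 84 | Week 13 Monday |
| #5 to #16, earliest | Week 10 Monday | 63 | 91 | Week 14 Monday |
| #5 to #16, if dosed Week 11 Friday | Week 11 Friday | 74 | 102 | Week 15 Friday |

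**Subjects with 28 days completed.**

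- Week 12, Monday or Tuesday: 1/16 = 6.25%
- Week 12, from Wednesday: 2/16 = 12.5%
- Week 13 Monday, when the table lets Group 4 start: 4/16 = 25%

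**Follow-up of #5 to #16 (12/16 = 75%).** Even if dosed on the first possible day (day 63), they have 83 − 63 = 20 days on Sunday of Week 12 and 90 − 63 = 27 days on Sunday of Week 13. Dosing later in Weeks 10 to 11 only shortens this: a subject dosed on Friday of Week 11 has 77 − 74 = 3 days on Monday of Week 12.

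**Position in the Group 3 cycle.** Cycle week = table week − 8 + 1.

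- Week 12 is cycle Week 5, short of the 7-week minimum in both section 5.1.1 and the dagger footnote.
- Week 14 is cycle Week 7, where section 5.1.1 begins preparing the DSMB review.
- Week 15 is cycle Week 8.

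**Earliest compliant review.** Week 14 if all of #5 to #16 are dosed in Week 10; Week 15 if any are dosed in Week 11. The table is 14 − 12 = 2 or 15 − 12 = 3 weeks early.

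**Sensitivity to the day count.** If the vaccination day counts as day 1 of 28, 27 elapsed days suffice. Then #3 and #4 qualify on Sunday of Week 12 (56 + 27 = 83), giving 4/16 on that one day. If instead the Day 29 visit may be held two days early, as the visit window in Table 2.1 allows, 26 elapsed days suffice. Then #3 and #4 qualify from Saturday of Week 12 (56 + 26 = 82), and #5 to #16 not before Saturday of Week 13 (63 + 26 = 89). Under neither reading can any of #5 to #16 qualify in Week 12.

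**The case against.** The case for leaving this alone concerns weight, not arithmetic.

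- **The rule itself is correct.** Section 5.1.1 states it explicitly, and the table shows minimums that its asterisk footnote lets the trial extend. A site could hold the review in Week 12 only by disregarding section 5.1.1. This stands as far as it goes: waiting complies with both texts. But the footnote makes a longer interval discretionary, whereas section 5.1.1 makes 28 days in all subjects a condition. A stated minimum that cannot meet the condition is still wrong. The DSMB charter may say more, but it is not available.
- **The primary endpoint is not harmed.** This is right. An early meeting removes no data from the final unsolicited-AE analysis; it affects only what the DSMB would have had before it.
- **Risk is low.** Ten subjects had already received 5 µg, section 5.7 says the later doses were lowered after those results, and the sentinel review and halt rules apply. This stands.
- **Dosing is finished.** SAP section 6.4 reports 53 subjects vaccinated, including all 16 in each of the 1 and 2 µg groups. Editing the table now changes no conduct. This stands and moves the useful part of the remedy to the report.
- **SAP section 9.2 already covers deviations.** In part: it sends all potential deviations to a data review meeting. Its listing is by subject, however, so a trial-level timing shortfall might not appear there.

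**Conclusion.** The inconsistency is real. At the minimum schedule in Table 2.2, a Week 12 DSMB review would have the required follow-up for 1 or 2 of 16 Group 3 subjects, and Group 4 could open in Week 13 with at most 4 of 16 complete on the Monday. The table's own Group 2 rows, its dagger footnote and the section 5.1.1 calendar all identify Week 12 as the wrong figure.

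The result rests on the dosing weeks as tabulated and on counting 28 elapsed days after dose 1. The weekday on which #5 to #16 are dosed does not matter. It is a definite error at a dose-escalation gate and worth correcting, but with low residual risk. The documents give no sign that the 28-day rule was breached in conduct.

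**What to change.** **In the clinical trial report (the part with practical value now).** State the date of the Group 3 DSMB review and how many of the 16 subjects then had 28 days of data after dose 1. If any were short, record this as a trial-level protocol deviation alongside the subject-level listing. Cost: one or two sentences and no new data.

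**In Table 2.2.** Replace the Week 12 entry with a DSMB decision not before 28 days after the first dose of the last Group 3 subject (earliest Week 14; Week 15 if dosing runs into Week 11). Relabel the 13 to 42 row so that Group 4 begins after a favourable Group 3 decision. This is two cells. It would formally be a protocol amendment, which under Appendix 8 needs authority and ethics approval if classed as substantial. With enrolment complete, the report statement may reasonably take its place.
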